1.2 RATIONALE FOR THE STUDY

A single centre, open-label, phase 2A/B pediatric epilepsy pilot study, evaluating safety, tolerability, and efficacy of VOR in a pediatric population with medically intractable epilepsy is proposed. Currently the incidence of medically refractory epilepsy remains unacceptably high and an unmet medical need exists for these patients. Newly identified treatment targets to control seizures are clearly required, however typically drug development takes greater than a decade to become available as a treatment option. Therefore, a strategy which rapidly identifies potential therapies

that can be rapidly tested in the clinical setting is paramount. The metabolism based discovery platform, initiated by our group is such a platform in which potential targets can be rapidly escalated to clinical trials in an accelerated knowledge translation manner. Via this platform, [name] *et al*³⁰ identified VOR as a potential viable therapy for the treatment of seizures in epilepsy. The pre-clinical work described above indicates outstanding efficacy and supports the potential benefit for VOR in potentially reducing refractory seizures in children with medically intractable epilepsy. VOR is currently approved by Health Canada for the treatment of CTCL malignancies. VOR demonstrated good tolerability in pediatric patients with various malignancies. When reviewing the safety and tolerability of VOR in the context of that of VPA and other AEDs, it is anticipated that tolerability of VOR will not be worse than that normally seen with currently approved AEDs in pediatric patients with medically refractory epilepsy.

To our knowledge – this proposed study is the first trial investigating VOR within a pediatric population with medically intractable epilepsy. In this proposed pilot trial, pediatric patients, aged 4 to 17 (inclusive) with medically intractable epilepsy will be given VOR, at a dose of 230 mg/m²/day for a duration of 6 weeks to determine safety, tolerability and efficacy at this dose in combination with standard of care anti-seizure medications.

SECTION 2.0: OBJECTIVES

2.1 PRIMARY OBJECTIVES

Characterize the safety and tolerability of 230 mg/m²/day VOR, administered orally, in a pediatric population with medically intractable epilepsy in combination with standard of care anti-seizure drugs.

2.2 SECONDARY OBJECTIVES

Evaluate the efficacy of 230 mg/m²/day of VOR, administered orally, in reducing seizures in a pediatric population with medically intractable epilepsy in combination with standard of care anti-seizure drugs.

SECTION 3: STUDY DESIGN

3.1 OVERVIEW OF STUDY DESIGN AND DOSING REGIMEN

The study will consist of a single centre, open-label Phase 2A/B pilot study evaluating the safety, tolerability, and efficacy, of VOR in a pediatric population with medically intractable epilepsy. Participants will be administered 230 mg/m²/day of VOR in addition to standard of care anti-seizure medication for a duration of 6 weeks.

3.1.1 DOSAGE

Participants will be administered 230 mg/m²/day of VOR in addition to standard of care anti-seizure medication for a duration of 6 weeks. The dosage was chosen based on the MTD of five Phase 1 trials, which included pediatric patients or were exclusively pediatric trials⁵⁰⁻⁵⁴.

Briefly, in a Phase 1 study, Fouladi et al⁵⁰, investigated VOR alone and in combination with 13cRA in children with recurrent or refractory malignancies (Part A – solid tumors; Part B – leukemia). Three dose levels were utilized: 180 mg/m² VOR; 180 mg/m² VOR + 13cRA; 230 mg/m² VOR; 300 mg/m² VOR). In the solid tumors group at a dose of 180 mg/m² VOR, one patient suffered an SAE, however this was deemed to not related to treatment. At the 230 mg/m²/d VOR dose level, there were no DLT in the first three patients enrolled. At 300 mg/m²/d DLT occurred in 2 of 6 patients but since the AEs were of different classes, the cohort was expanded to six additional evaluable patients. At this dose, 2 patients had DLT thereby exceeding the MTD, therefore three additional patients were subsequently enrolled at the 230 mg/m². In this cohort, only one experienced a DLT, defining 230 mg/m²/d as the MTD and recommended phase II dose for children with solid tumors. The recommended phase II dose was then trialed in the refractory leukemia group. Two of the first five patients experienced DLT, therefore this dose did not appear tolerable in children with refractory leukemia; no other dose finding was attempted in this population.

In a Phase 1 study, Hummel et al⁵¹ investigated VOR in combination with TEM in children with recurrent or refractory brain or spinal cord tumors. Three dose levels were tested: 230 mg/m² VOR + 150 mg/m² TEM; 300 mg/m² VOR + 150 mg/m² TEM; 300 mg/m² VOR + 200 mg/m² TEM. There were no DLTs at Dose level 1 or 2. At dose 3, 4 patients had DLTs, therefore the recommended phase 2 dose for the combination of VOR and TEM as 300 mg/m² VOR + 150 mg/m² TEM.

In a Phase 1 study, Muscal et al⁵² investigated VOR in combination with BOR in children with recurrent or refractory solid tumors, including CNS tumors. Three dose levels were tested: 180 mg/m² VOR + 1.3 mg/m²/d BOR; 230 mg/m² VOR + 1.3 mg/m²/d BOR; 300 mg/m² VOR + 1.3 mg/m²/d BOR. At the third dose level, 2 patients experienced DLTs, thus dose level 2 (230 mg/m² + 1.3 mg/m²/d BOR) is the recommended phase 2 dose.

Burke et al⁵³ performed a pilot study investigating the combination of DEC and VOR followed by standard re-induction chemotherapy in patients with relapse or refractory acute lymphoblastic leukemia. The only dosage tested was 230 mg/m² VOR + 15 mg/m² DEC. The choice of this dosage was based on prior Phase 1 studies identifying the MTD for these agents. 12 patients completed the full 4 days of treatment and were evaluable for toxicity assessment; 8 patients completed full protocol therapy and end of course evaluation; the one patient who did not complete the 4 days died of progressive disease on Day 4; the other 4 patients did not complete protocol therapy due to progressive disease , toxic

death; family decision to stop due to toxicity; patient found to have leukemic involvement and physician elected to change treatment .

Dubois et al⁵⁴ conducted a phase I multicenter clinical trial conducted through the New Approaches to Neuroblastoma Therapy (NANT) consortium with the primary objective to determine the MTD of vorinostat and MIBG when used in combination. Five dosage levels were assessed: 8 mCi/kg ¹³¹I-MIBG + 180 mg/m² VOR; 12 mCi/kg ¹³¹I-MIBG + 180 mg/m² VOR; 12 mCi/kg ¹³¹I-MIBG + 230 mg/m² VOR; 15 mCi/kg ¹³¹I-MIBG + 230 mg/m² VOR; 18 mCi/kg ¹³¹I-MIBG + 230 mg/m² VOR. There was no DLT at dose levels 1-3; at dose level 4, there was 1 DLT; and at dose level 5 – 2 patients had DLT. Due to 2/2 patients with DLT at Dose 5, the dose was de-escalated to 18 mCi/kg ¹³¹I-MIBG + 180 mg/m² VOR because there were no DLT at that dose level. Therefore the MTD is 18 mCi/kg ¹³¹I-MIBG + 180 mg/m²VOR; this is because MIBG is the main active agent in this combination and VOR acts a radiation sensitizer; the usual maximum feasible dose is 18 mCi/kg

3.1.2 PHASES OF STUDY

There are three phases to the study.

Phase 1: Screening period

During this phase, participants will be screened for study eligibility, which will last a total of 4 weeks. This will include several baseline investigations including full review of medical history and current medications, seizure frequency, physical examination, vital signs, laboratory safety testing, pregnancy testing for eligible patients, and electrocardiogram (ECG) (see Section 5 Schedule of Assessments and Procedures for complete list of screening procedures). In addition, baseline seizure frequency will be determined during this period. Clinically stable participants, fulfilling all eligibility criteria (see sections 4.2 and 4.3) will be enrolled in the treatment period of the study.

Phase 2: Treatment period

The duration of the treatment period will be 6 weeks. VOR will be given as fixed doses of 230 mg/m²/day. Following the enrollment visit, participants will visit the clinic for 2 more visits every 2 weeks, plus an end of treatment (EOT) visit (see Section 5.1 for detailed schedule). Participants may be seen more frequently for unscheduled visits for follow up of AEs, etc. as per the investigator's discretion. Study visits will include a physical examination, height and weight measurement, vital signs, pregnancy testing (required patients only). Safety monitoring during the treatment period will include laboratory safety testing and ECG. Investigators will review current medications, AEs, seizure diary/frequency at each visit. Investigators will assess study medication adherence at all visits; unused study medication will be returned to site at each visit and new study medication will be dispensed by local pharmacy, as recommended by the investigator. Unused study medication will be destroyed as per local standard operating procedures. All assessments and visit procedures will occur as stipulated in Section 5: Schedule of Assessments and Procedures.

Phase 3: Follow-up period

A safety follow-visit (SFU) will take place 6 weeks after the EOT Visit. The SFU visit will include a physical examination, height and weight measurement, vital signs. Safety monitoring for this visit will include laboratory safety testing and ECG. Investigators will review AEs since last visit and seizure diary/frequency. Any ongoing AEs will be followed by the investigator until resolution or stability.

3.1.2 END OF STUDY

The end of the study is defined as the date of the last patient's last visit, or the date at which the last data point, required for analysis, is completed, whichever date is later.

3.2 RATIONALE FOR STUDY DESIGN

The pre-clinical data for VOR is highly suggestive of a potential novel therapy for the treatment of medically intractable epilepsy. However, VOR is currently approved only for the treatment of cutaneous manifestations in patients with advanced CTCL who have progressive, persistent or recurrent disease subsequent to prior systemic therapies. A safety/efficacy trial of VOR in a population with medically intractable epilepsy is largely warranted, given the existing need for additional therapeutic strategies. The target population will consist of pediatric patients with medically intractable epilepsy, recruited from the Alberta Children's Hospital (ACH) Neurology Outpatient Clinic, with medically intractable epilepsy despite exhaustive treatment with current standard therapies, who would be anticipated to benefit from a novel intervention strategy.

The primary endpoints of this study are the safety & tolerability of VOR in pediatric patients with medically intractable epilepsy. The secondary endpoints of this study is the efficacy of VOR in reducing seizure frequency in this population pool. Participants will receive 230 mg/m²/day of VOR in addition to standard of care anti-seizure medication for a duration of 6 weeks, to evaluate the risk/benefit of VOR at this dosage on top of standard of care anti-seizure treatment.

The proposed study design will allow for the study objectives to be met within the context of a typical Canadian clinical epilepsy treatment centre. Completion of this pilot study in this population will begin to indicate the safety & efficacy profile of VOR at a dosage of 230 mg/m²/day as a potential therapy for the treatment of seizures, and based on findings may justify a larger randomized study to further investigate this potential avenue in children with medically intractable epilepsy in a rapidly translational manner.

3.3 NUMBER OF SUBJECTS

12 pediatric patients meeting the criteria of medically intractable epilepsy in addition to the other eligibility criteria, recruited from the ACH Neurology Outpatient Clinic will be enrolled in study.

SECTION 4: STUDY POPULATION

4.1 OVERVIEW

The target population will consist of pediatric patients with medically intractable epilepsy, recruited from the ACH Neurology Outpatient Clinic, who continue to experience seizures despite exhaustive treatment with current standard therapies, and anticipated to possibly benefit from a novel intervention strategy.

4.2 INCLUSION CRITERIA

Patients must meet **ALL** of the following criteria in order to be eligible for this study:

1. Males or females aged 2 – 17 years (inclusive)
2. Medically intractable epilepsy, defined as having failed at least 2 standard anti-seizures therapies and experiencing at least 3 motor seizures per week, separated by at least 24 hours that are quantifiable by observation (e.g. discrete episodes of motor activity). Participants experiencing other seizure types in addition to motor seizures may also be enrolled but must meet the minimal requirement for motor seizures.
3. Ability and willingness of family and/or caregiver (when appropriate) to give written informed consent and to comply with requirement of the study
4. Adequate bone marrow function (defined as an absolute neutrophil count (ANC) of $\geq 2 \times 10^9/L$; platelet count of $\geq 150 \times 10^9/L$; hemoglobin of ≥ 110 g/L [3-11 years], ≥ 120 g/L [females 12 years or over], ≥ 125 g/L [males 12-14 years], ≥ 137 g/L [males 15 years or older])
5. Adequate renal function (defined as serum creatinine $< 1.5X$ age-adjusted upper limit of normal [ULN], or glomerular filtration rate ≥ 70 mL/min/1.73 m²)
6. Adequate hepatic function (defined as total bilirubin < 1.5 times ULN, and alanine aminotransferase [ALT] and aspartate transaminase [AST] < 3 times ULN, and albumin > 33 g/L)
7. Corrected QT (QTc) interval of < 450 msec
8. Prothrombin time (PTT) < 1.5 ULN/International Normalized Ratio (INR) < 1.5 ULN
9. Participants on corticosteroids must be taking a stable or decreasing dose for at least 7 days prior to enrollment

4.3 EXCLUSION CRITERIA

Patients meeting any of the following criteria by the day of enrollment are **NOT** eligible for this study

1. Treatment with valproic acid or other HDACi class drugs within at least the last 3 months at time of screening
2. Enzyme-inducing AEDs (including oxcarbazepine (Trileptal), phenobarbital, phenytoin (Dilantin), topiramate (Topamax))
3. Coumarin-derivative anti-coagulants
4. Participants being considered for surgery for management of seizures during screening or who will be receiving surgery during for management of seizures during study period (includes all neurosurgery for the management of seizures or device implantation for the management of seizures)
5. Neurosurgery within the past 12 months
6. Use of Vagus Nerve Stimulator (VNS) where settings have not been stable for at least 6 months

7. Planned surgery or other invasive medical treatment during screening or during treatment period
8. Hypokalemia or hypomagnesemia
9. Participants starting or currently on any neurometabolic diet (including but not limited to ketogenic diet; medium-chain triglyceride diet; modified Atkins diet; low glycemic index diet) during study
10. History of non-catheter related deep venous thrombosis
11. Pleural effusion
12. Malignancy within the past 5 years.
13. Any serious medical condition that according to the investigator could interfere with the conduct of the study
14. Serious comorbid disease in which the life expectancy of the patient is shorter than the duration of the trial
15. Unwillingness or inability to comply with study requirements
16. Positive pregnancy test, lactating females or heterosexually active participants not willing to use highly effective methods of contraception (See [Section 4.6](#))
17. Participation in any clinical trial with an investigational drug, or therapy not approved by Health Canada, within one month prior to screening

4.4 DIAGNOSTIC CRITERIA FOR MEDICALLY INTRACTABLE EPILEPSY

Medically intractable epilepsy as defined by the ILAE 2010 task force as experiencing at least 3 motor seizures per week, separated by at least 24 hours that are quantifiable by observation (e.g. discrete episodes of motor activity), despite treatment with standard clinical therapies. Participants experiencing other seizure types in addition to motor seizures may also be enrolled but must meet the minimal requirement for motor seizures.

4.5 CONCOMITANT MEDICATIONS AND TREATMENTS

4.5.1 PROHIBITED CONCOMITANT MEDICATIONS AND TREATMENTS

Participants may not be initiated on the following treatments or therapies during the study:

- neurometabolic diets including but not limited to ketogenic diet; medium-chain triglyceride diet; modified Atkins diet; low glycemic index diet
- surgery for the management of seizures; patients who have previously had surgery for the treatment of seizures may participate as long as surgery was completed a minimum of 12 months at time of enrolment
- device implantation or use of other devices for the management of seizures; patients may be entered if device was implanted a minimum of 12 months prior to enrolment and settings have remained stable for a minimum of 6 months at time of enrollment
- Valproic acid/valproate/divalproex sodium or other Histone Deacetylase (HDAC) Inhibitors
- Enzyme inducing AEDs, including oxcarbazepine (Trileptal), phenobarbital, phenytoin (Dilantin), topiramate (Topamax)
- Coumarin-derivative Anticoagulants
- Any other therapy that is experimental or not approved by Health Canada (e.g. cannabidiol oil)

4.5.2 PERMITTED CONCOMITTANT MEDICATIONS

The use of any concomitant medication will be recorded in the study record.

Treatment for Epilepsy

Patients will continue on their evidence-based medical care for epilepsy as described in regional guidelines and institutional care pathways. All contemporary evidence-based medical care for ACH should be initiated as early as possible during the screening period to allow time for stabilization of the treatment effects before enrollment.

Investigators will monitor patients/treat patients as per normal clinical practice with regard to these medications for the duration of the study. Therapy dose adjustments for the treatment of epilepsy will be left to the investigators' discretion, however it is highly recommended that adjustments be minimized throughout the period of the study.

Patients who have a VNS device implanted for the management of seizures, and whose device treatment parameters are optimized and stable for the last 6 months may participate in study. Changes to the device treatment parameters should be avoided during the study.

Permitted medications with special precautions

Other QT/QTc Prolonging Drugs:

As per the product insert, concomitant use of VOR with another QTc prolonging drug may have an additive effect on QTc interval, and the concomitant use of VOR with another QT/QTc-prolonging drug should be avoided. This includes: Class IA antiarrhythmics; Class III antiarrhythmics; Class IC antiarrhythmics; anthracyclines; tyrosine kinase inhibitors antipsychotics; antidepressants; opioids; macrolide antibiotics and analogues; quinolone antibiotics; pentamidine; antimalarials; azole antifungals; domperidone; 5-HT₃ receptor antagonists; tacrolimus; beta-2 adrenoceptor agonists. In the case where a participant is taking a QT/QTc prolonging drug during treatment phase, it is recommended that an ECG be conducted within one week of starting VOR and the QT/QTc prolonging drug if the next protocol ECG is longer than one week. Additional ECGs should be conducted as per the investigator's discretion if the participant is exhibiting signs of QT/QTc prolongation.

Drugs that Disrupt Electrolyte Levels:

Electrolyte imbalance such as hypokalemia increases the risk of QTc interval prolongation, therefore the use of VOR with drugs disrupting electrolyte level is discouraged. Drugs that can disrupt electrolyte levels include, but is not limited to, the following: loop, thiazide, and related diuretics; laxatives and enemas; amphotericin B; and high dose corticosteroids. Additional laboratory testing may be conducted as per the investigator's discretion if the participant is exhibiting signs of disruption of electrolyte levels.

4.6 CONTRACEPTION PROTECTION

Heterosexually active females and males (partners of male participants, as appropriate) must use an acceptable method of contraception to prevent pregnancy. Acceptable methods of contraception include the following:

- Abstinence
- Barrier type devices (e.g. female condom, diaphragm and contraceptive sponge) used ONLY in combination with a spermicide
- Intra-uterine devices
- Oral contraceptive agents started at least 90 days before start of study
- Depo-Provera (medroxyprogesterone acetate)
- Levonorgestrel implants
- Naturally or surgically sterile females (amenorrheic for at least 1 year and no record of conception for naturally sterile persons)
- Male partner is sterile and is the only sexual partner.

4.7 CRITERIA FOR PREMATURE WITHDRAWAL

Participants have the right to refuse treatment or completely withdraw from the study at any time for any reason. The investigator also has the right to discontinue treatment and withdraw participants from the study treatment in the event of intercurrent illness, AE, treatment failure, protocol violations, administrative reasons, or other reasons deemed necessary by the investigator.

Participants with significant drug compliance issues or safety monitoring compliance issues, not related to AEs will be withdrawn from the treatment phase of the study by the investigator and an EOT visit as well as an SFU visit will be attempted to be performed in all cases.

If the participant withdraws from study treatment only, they will undergo an EOT visit and SFU visit. If the reason for removal of a participant from the study is an AE or an abnormal laboratory test result, the principal specific event or test will be recorded in the study record. If the participant explicitly withdraws consent for additional follow-up, the participant will be asked to undergo a phone SFU visit at the absolute minimum. In addition, all efforts will be made to complete and report the observations prior to withdrawal as thoroughly as possible. A complete final evaluation at the time of the participant's withdrawal should be made with an explanation of why the participant is withdrawing from the study. In the event that a participant is lost to follow up, the last assumed day of medication will be the last day for which number of doses was provided. An attempt will be made to contact participants, via provided phone, email, and registered letter to the address provided. All attempts to contact will be recorded in the study record. In the event that all attempts for contact fail, a chart review and review of NetCare will done at 6 weeks following the last assumed day of medication.

4.8 REPLACEMENT POLICY

PROTOCOL: VOR-17-2471
Version 2: 2018-07-18

Participants who withdraw/are withdrawn or discontinue study medication will not be replaced. Participants who discontinue medication/withdraw from study for non-safety issues within 14 days of commencing study medication will not be included in the final analysis.

SECTION 5: SCHEDULE OF ASSESSMENTS AND PROCEDURES

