5.1.4 SAFETY FOLLOWUP

An SFU for all participants, including patients prematurely withdrawn from treatment, will be conducted 6 weeks after the EOT visit. This visit will include:

- Physical examination
- Complete neurological examination
- Anthropometrics
- Vital signs
- Laboratory monitoring. Participants will be contacted with results requiring intervention
- Pregnancy test: a serum pregnancy test will be taken for applicable participants.
- Concomitant medications
- Seizure Frequency
- Review of Adverse Events
- Review of seizure frequency
- ECG: may be collected within 1 week prior to study visit.

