7.1.3 TREATMENT AND FOLLOW UP OF AEs

AEs will be followed up until they have returned to baseline status or stabilized. Details of follow up will be recorded in the study record including if return to baseline status or stabilization cannot be achieved.

In the event of medically significant unexplained abnormal laboratory test values, the tests will be repeated and followed up until they have returned to the normal range or the baseline value and/or an adequate explanation of the abnormality is found. All details will be included in the study record.

If the study drug is discontinued due to an AE or a laboratory abnormality, the study medication will not be reinstated. If the investigator decides to discontinue study drug treatment, the rationale for their decision will be provided in the AE comment/SAE narrative field of the study record.

Study drug will be discontinued in the presence of an SAE that is deemed to be related or possibly related. Thromboembolic events or any event which a participant finds intolerable, which cannot be mitigated with therapy, will be cause for VOR discontinuation. Participants experiencing a $\geq 50\%$ increase in seizure frequency, as compared to baseline at any time during the treatment period will be discontinued from study medication. Additionally, participants presenting with status epilepticus at any time during the treatment period will be discontinued from study medication.

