8.1 PRIMARY AND SECONDARY STUDY ENDPOINTS

8.1.1 PRIMARY ENDPOINTS

The primary endpoint for this study will be the incidence of related AEs and SAEs, and discontinuation of therapy due to intolerable AEs.

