8.2.2 ANALYSIS

8.2.2.1. SAFETY & TOLERABILITY ANALYSIS

Safety and tolerability will be assessed by calculating the incidence rate of AEs per number of drug days from the time medication is started through to the completion of the SFU (or 42 days following the last dose of study medication). This will be done for the following time points: 14 days following drug initiation; 30 days following drug initiation; 42 days following drug initiation; and 42 days following drug discontinuation. AEs will be further stratified by mild/moderate AEs, severe AEs, and SAEs, as well as project specific AEs (thromboembolism, hyperglycemia, gastrointestinal disturbances, dehydration, hematologic disturbances, QT/QTc prolongation).

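### Section 4.8 drops dosed children who stop within 14 days for non-safety reasons from the final analysis, and Section 8 defines no safety population or responder denominator that keeps them in

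*Combined protocol and SAP*

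**What the plan says.** Section 3.3 plans 12 children, and Section 4.8 says that withdrawals are not replaced. Section 4.8 then adds: "Participants who discontinue medication/withdraw from study for non-safety issues within 14 days of commencing study medication will not be included in the final analysis". It does not limit this to efficacy, and neither it nor any other section says what counts as a non-safety issue.

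Section 8.1.1 sets the primary endpoint: "The primary endpoint for this study will be the incidence of related AEs and SAEs, and discontinuation of therapy due to intolerable AEs". Section 8.2.2.1 assesses safety by "calculating the incidence rate of AEs per number of drug days from the time medication is started through to the completion of the SFU", with summaries at 14, 30 and 42 days after starting drug and 42 days after stopping it. Section 8.2.2.2 gives a responder proportion at 6 weeks against baseline. Neither section names the participants who contribute, and Section 8.2.2.2 has no rule for a child who stops before week 6.

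Several passages bear on who is affected:

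- Section 4.7 lets the investigator withdraw a child "in the event of intercurrent illness, AE, treatment failure, protocol violations, administrative reasons", so treatment failure and protocol violations are listed apart from adverse events. Section 6.3 also allows withdrawal for non-compliance in the first 14 days.
- Section 7.1.3 says: "Study drug will be discontinued in the presence of an SAE that is deemed to be related or possibly related". It also requires a stop for a seizure increase of 50% or more, and "participants presenting with status epilepticus at any time during the treatment period will be discontinued from study medication".
- Follow-up continues after an early stop. Section 4.7: "If the participant withdraws from study treatment only, they will undergo an EOT visit and SFU visit". Section 5.1.4: "An SFU for all participants, including patients prematurely withdrawn from treatment, will be conducted 6 weeks after the EOT visit".

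**The concern.** The excluded children have taken the drug. In a trial whose main purpose is to describe safety, in a disease where the drug has not been tested before, each of 12 children is 8.3% of the denominator (1/12).

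Read literally, Section 4.8 takes these children's drug-days and events out of the primary summaries. What can be lost is non-serious related AEs, SAEs that begin after a non-safety stop, and SAEs judged unrelated. Whether the last group belongs to the primary endpoint depends on whether the word related in Section 8.1.1 qualifies SAEs as well as AEs, which is unclear. Sections 5.2.1 and 8.2.2.1 count AEs and SAEs without that limit.

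The trial is open-label, so whoever classifies a stop as safety or non-safety already knows how the child has done. For the secondary endpoint, the rule can remove children who would otherwise count as non-responders, such as a treatment failure or a non-compliant child withdrawn early.

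**Working it through.** The plan has no figure to reproduce. Section 8.2.1 rests the sample size on feasibility and cost, and the documents give no expected number of early stops.

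**Inputs.** N = 12 (Section 3.3); no replacement (Section 4.8); time points of 14 and 42 days (Section 8.2.2.1). Assumptions: k = 1, 2 or 3 children excluded; 7 days on drug for each; retained children on drug throughout; all event counts.

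**Step 1: does Section 8 restore the excluded children?** Section 8.2.2.1 starts counting when medication starts. That sets a time window, not a population. Section 8.2.2.2 sets a response threshold and a time point, not a denominator. Sections 4.7 and 5.1.4 ensure that data are collected, but they do not put the child into an analysis. Nothing overrides Section 4.8.

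**Step 2: drug-days lost by day D** = 7k / [D(12 − k) + 7k].

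| | k = 1 | k = 2 | k = 3 |
|---|---|---|---|
| D = 14 | 7/161 = 4.3% | 14/154 = 9.1% | 21/147 = 14.3% |
| D = 42 | 7/469 = 1.5% | 14/434 = 3.2% | 21/399 = 5.3% |

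**Step 3: direction of the AE rate.** Take k = 2 at day 14, with 8 AEs in the 10 retained children. After exclusion the rate is 8/140 = 5.71 per 100 drug-days. In all dosed children it is 8/154 = 5.19 if the excluded two had no AE, or 10/154 = 6.49 if they had two. The rule can push the rate either way.

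**Step 4: proportions**, x/12 against x/(12 − k).

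| | All 12 | k = 1 | k = 2 | k = 3 |
|---|---|---|---|---|
| One SAE, in a retained child | 8.3% | 9.1% | 10.0% | 11.1% |
| Three stops for intolerable AEs | 25.0% | 27.3% | 30.0% | 33.3% |
| Four responders, excluded children non-responders | 33.3% | 36.4% | 40.0% | 44.4% |

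- If the only SAE is in one excluded child, 1/12 = 8.3% (exact 95% CI 0.2% to 38.5%) is reported as 0/11 = 0% (0% to 28.5%).
- If one of four AE stops is labelled non-safety, 4/12 = 33.3% becomes 3/11 = 27.3%.
- With no AE stops, the discontinuation proportion is 0% either way.

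**The case against.** The strongest defence is that the rule keeps the children who matter most for safety. A child with a related or possibly related SAE on drug must stop under Section 7.1.3, is therefore a safety stop, and stays in. Stops for status epilepticus or a large rise in seizures are most naturally read the same way, though the protocol does not label them. SAEs go to the ethics board and Health Canada (Sections 5.3.1 and 7.2.2), AEs are collected for 6 weeks after the last dose (Section 7.2.1), and Section 4.7 asks that observations before withdrawal be completed and reported. This is also a small pilot with no hypothesis test, and no child may ever meet the exclusion. All of that stands and limits the reach of the point. None of it defines an analysis population.

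Three stronger readings are tempting, and the documents do not support them:

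- *The rule hides drug-related SAEs.* Those arising on drug lead to a safety stop and are retained. A related SAE is lost only if it begins after a non-safety stop. The 1/12 to 0/11 example bears on the primary endpoint for an unrelated SAE only if related does not qualify SAEs in Section 8.1.1.
- *Sections 4.8 and 8.2.2.1 contradict each other.* Section 8.2.2.1 names no population, so the fault is an exclusion rule with nothing to override it.
- *The rule makes the drug look safer.* The AE and SAE rates can move either way, and with correctly classified stops the AE-discontinuation proportion rises or stays at zero.

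The efficacy effect is also bounded. The first compliance audit is at week 2, plus or minus 2 days (Table 5), so some non-compliance withdrawals fall after day 14. Purely administrative stops need not bias the response rate.

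**Conclusion.** The point holds and should be fixed before analysis. As written, Section 4.8 removes dosed children from the primary safety summaries of a 12-child safety trial, and Section 8 does not put them back. The defect is in what is reported, not in safety oversight.

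Its size depends on a number that the documents do not give. In the plan's own unit, one to three exclusions at 7 days each cost 4.3% to 14.3% of drug-days at day 14, falling to 1.5% to 5.3% at day 42. The per-child proportions are more sensitive, because one child can decide whether any SAE is shown at all. Section 5.2.1's figures of 10% for SAEs and 30% for AE discontinuations are expectations and not decision rules, so crossing them has no formal consequence.

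The importance rests on the safety part. The possible inflation of the responder proportion, by 12/(12 − k) = 1.09, 1.20 or 1.33 when the excluded children would be non-responders, concerns a secondary endpoint and would not carry the point alone.

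**What to change.** Delete the 14-day exclusion from Section 4.8 as a rule for the final analysis. Add to Section 8.2.2:

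*Safety and tolerability are analysed in every participant who took at least one dose of study drug. The responder denominator is all dosed participants with a baseline seizure count. A participant who permanently stops study drug before completing the planned 6-week course counts as a non-responder; the date of the EOT visit within its window does not make a completer a non-responder.*

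Report the responder proportion in the set that Section 4.8 now defines, leaving out only non-safety stops within 14 days, as a labelled sensitivity analysis. A set of children treated for at least 14 days would not serve, because it would also drop the early safety stops that Section 4.8 keeps. List the day and reason of each early stop, and clarify in Section 8.1.1 whether related applies to SAEs.

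Counting every early stop as a non-responder is a defensible convention, not the only one. It also closes a separate gap, the missing responder rule for stops after day 14.

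The cost is one deleted sentence and a short paragraph. No new data collection is needed, since follow-up of these children is already planned, although a child who withdraws consent to follow-up may give only a telephone contact. The response rate may be slightly lower and administrative stops will count against it; the sensitivity analysis shows how much the early ones matter.
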